5.2.2 Definition of Dose Limiting Toxicity

DLT's will be defined from toxicities observed during the first cycle of treatment (21 days) for each dose level. See Section 5.2.4 for rules on replacement of subjects in the DLT period. The occurrence of any of the following toxicities during Cycle 1, if assessed by the Investigator to be possibly, probably or definitely related to MK-1966 or SD-101 in Arm A, will be considered a DLT:

1. Grade 4 non-hematologic toxicity (not laboratory)
2. Grade 4 hematologic toxicity lasting \geq 7 days, except thrombocytopenia
 - a. Grade 4 thrombocytopenia of any duration
 - b. Grade 3 thrombocytopenia is a DLT if associated with bleeding:
3. Grade 3 non-hematologic toxicity (not laboratory) lasting $>$ 3 days despite optimal supportive care. Grade 3 nausea or vomiting will be considered a DLT if lasting more than 3 days despite optimal supportive care.
4. Any Grade 3 or Grade 4 non-hematologic laboratory abnormality, if
 - medical intervention is required, or
 - the abnormality leads to hospitalization, or
 - the abnormality persists for $>$ 1 week
5. Febrile neutropenia Grade 3 or Grade 4
6. Any drug-related AE which caused subject to discontinue treatment during Cycle 1
7. Grade 5 toxicity
8. Delay in initiation of Cycle 2 for $>$ 2 weeks due to study drug-related toxicity

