5.2.1.2 Dose Escalation

Enrollment to Arm A, (MK-1966 with SD-101) will begin at the 70 mg for MK-1966 and 1 mg for SD-101. The initial dose combination of SD-101 and MK-1966 will test the tolerability of administering both agents in subjects with advanced tumors. The following three dosing cohorts were chosen with administration of the higher fixed dose of SD-101 to increase immune activation combined with escalating doses of MK-1966. All dose levels in Part A will follow 3+3 design. Dose escalation of MK-1966 will continue to identify a preliminary MTD or MAD.

The dosing for each cohort is as follows:

- 1) 1 mg SD-101 intratumorally and 70 mg MK-1966 intravenously
- 2) 4 mg SD-101 intratumorally and 70 mg MK-1966 intravenously
- 3) 4 mg SD-101 intratumorally and 210 mg MK-1966 intravenously
- 4) 4 mg SD-101 intratumorally and 700 mg MK-1966 intravenously

Note, if the 4 mg SD-101 and 70 mg MK-1966 combination (cohort 2) is not tolerated, then SD-101 will be de-escalated to a 1 mg dose for subsequent cohorts (3 & 4). The study will include up to four dosing cohorts for SD-101 and MK-1966.

5.2.1.2.1 3+3 Dose Escalation

During 3+3 dose escalation, at least 2 days of observation will occur between each of the first 3 subjects at each dose level.

Dose escalation will increase in increments of approximately 3 fold.

The rules applied for the preliminary dose finding using the 3+3 design are as follows:

An initial cohort of 3 subjects is enrolled.

- If 0/3 subjects develops a DLT, escalation to the next dose will occur.
- If 1/3 subjects develops a DLT, another 3 subjects will be enrolled at this dose level.
 - If 0 of the 3 new subjects develops a DLT (for a total of 1/6 subjects with a DLT at this dose level), escalation to the next dose level will occur.

- If ≥ 1 of the 3 new subjects develops a DLT (for a total of $\geq 2/6$ subjects with a DLT at this dose level), the dose escalation stage of the trial will be terminated.

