7.1.2 Clinical Procedures/Assessments

7.1.2.1 Adverse Event (AE) Monitoring

The Investigator or qualified designee will assess each subject to evaluate for potential new or worsening AEs as specified in the Trial Flow Chart and more frequently if clinically indicated. Adverse events will be graded according to NCI CTCAE Version 4. Toxicities will be characterized in terms of seriousness, causality, toxicity grade and action taken with regard to trial treatment.

This is a dose escalation trial to establish the MTD of MK-1966 in combination with SD-101; therefore, each dose escalation will be based on the safety and tolerability experienced by subjects at each dose level. The safety and tolerability of each cohort for the DLT evaluation period will be reviewed prior to the start of the next cohort. The Sponsor and the Principal Investigators will review the safety and tolerability of each trial treatment, the appropriateness of dose escalation, when each cohort is completed and the next cohort is opened for enrollment. Frequency of these communications will depend on the enrollment of each cohort, as well as any potential new information regarding a safety concern in this trial or other relevant trials.

As a Phase 1 trial, there is no plan for an external safety reviewer. Data from individual subjects will be closely followed on an ongoing basis by the Principal Investigator and the Sponsor.

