8.5 Analysis Populations

8.5.1 Safety Analysis Populations

The All-Patients-as-Treated (APaT) population will be used for the analysis of safety data in this study. The APaT population consists of all subjects who received at least one dose of study treatment. In case of treatment administration errors, subjects will be analyzed according to the treatment they actually received. For DLT evaluation, APaT subjects that were observed for safety for 21 days after the first dose of assigned treatment or experienced a DLT prior to 21 days after the first dose of assigned treatment will be used.

At least one laboratory or vital sign measurement obtained subsequent to at least one dose of study treatment is required for inclusion in the analysis of each specific parameter. To assess change from baseline, a baseline measurement is also required.

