8.6.3.5 Sample Size and Power Calculations

Dose Escalation and Dose Confirmation/Expansion

The primary purpose of the dose escalation and dose confirmation/expansion parts of the trial is to investigate the safety and tolerability of MK-1966 co-administered with SD-101 in adult subjects with advanced malignancies (Parts A-C) and to establish RPTD for MK-1966 co-administered with SD-101.

The final number of subjects enrolled in the dose escalation and confirmation/expansion parts of the study will depend on the empirical safety (DLT) observations, in particular, at what dose is identified as the RPTD. Sample sizes for a few possible scenarios as well as the

estimated time required to enroll all subjects and the time required to determine the MTD are provided below. The time required to estimate the MTD is the time from the first subject's first dose to the end of the 3-week observation period following the first dose of the last subject enrolled in the dose confirmation/expansion part. The study duration is derived as the time from the first subject's first dose to the end of 6-month treatment period following the enrollment of the last subject.

The enrollment time was conservatively estimated assuming that during 3+3 parts and the dose confirmation/expansion a subject can be enrolled every week. The sample size for each malignancy is 20 subjects, for the purpose of efficacy assessment in exploratory objectives.

Scenario 1. No DLTs during Parts A-C. For MK-1966 with SD-101, in a scenario where no DLTs are encountered during the dose escalation and confirmation/expansion parts so that Part A continues to the highest dose in [Table 5](#), the sample size to determine the MTD is 32 subjects (12 in Part A, 20 from Parts B and C). The total sample size is 52 subjects (12 subjects across 3 doses in Part A, 20 subjects on RPTD in Part B, and another 20 subjects on RPTD in Part C).

It will take 52 weeks to enroll 52 subjects in Parts A-C. Thus, in this scenario the enrollment time across Parts A-C is 52 weeks and the time required to determine the MTD is 35 weeks for 32 subjects. The study duration then is approximately 52 weeks + 24 weeks or 1.8 years. If dose escalation stops at a dose below the highest dose, the study might require less than 52 subjects and the enrollment duration shorter than 52 weeks.

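### DLT criterion 8 (Cycle 2 delayed more than 2 weeks) cannot be met before Day 37, but the DLT window is 21 days and no rule makes a Part A cohort decision wait for a subject on a drug-related hold

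*Combined protocol and SAP*

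**What the plan says.** Section 5.2.2 states that DLTs "will be defined from toxicities observed during the first cycle of treatment (21 days) for each dose level", and the sentence that introduces the list again ties the events to Cycle 1. Criterion 8 on that list is a "Delay in initiation of Cycle 2 for" more than 2 weeks because of drug-related toxicity. Criterion 6 is "Any drug-related AE which caused subject to discontinue treatment during Cycle 1".

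The flow chart (section 6.0) puts Cycle 2 Day 1 on Day 22, and section 5.2.5 allows it up to 1 day late.

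On timing, section 7.1.2.1 says: "The safety and tolerability of each cohort for the DLT evaluation period will be reviewed prior to the start of the next cohort". Section 8.5.1 counts a subject for DLT evaluation once "observed for safety for 21 days after the first dose of assigned treatment", or on a DLT before then. In section 5.2.1.2.1 the rule is: "If 0/3 subjects develops a DLT, escalation to the next dose will occur". A result of 1/3 calls for three more subjects, 1/6 escalates and 2/6 stops. The only waiting time stated there is that "at least 2 days of observation will occur between each of the first 3 subjects at each dose level".

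Table 7 holds both drugs for several drug-related Grade 2 events (diarrhea/colitis, AST/ALT/bilirubin, pneumonitis, renal failure or nephritis) and allows up to 12 weeks from the last dose for resolution.

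**The concern.** The list contains an event that needs more time than the window allows. If the 21 days bind strictly, criterion 8 can never be met and has no effect. If criterion 8 is meant to count, for example because the toxicity began in Cycle 1 and the delay is its consequence, it is established only after the point at which the plan lets the cohort be judged. Nothing in Part A defers the decision for a subject on hold, and nothing says what to do when a criterion 8 DLT appears after escalation.

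DLT is the primary endpoint (section 8.4.2) and drives a first-in-human escalation. Each step raises MK-1966 about 3-fold (70 to 210 to 700 mg) or, from cohort 1 to cohort 2, SD-101 4-fold (1 to 4 mg). Three subjects could receive the next level on a count that the plan's own definition later changes.

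**Working it through.** **1. The plan's own timeline.** Section 8.6.3.5 counts time to the MTD up to the "end of the 3-week observation period following the first dose of the last subject enrolled", at one subject per week. Scenario 1: 32 + 3 = 35 weeks. Scenario 2: 44 + 3 = 47 weeks. Both stated figures reproduce.

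**2. Earliest day for criterion 8.** Cycle 2 Day 1 = 1 + 21 = Day 22. A delay of exactly 14 days is Day 22 + 14 = Day 36. A delay of more than 14 days begins on Day 37. Gap from the end of the window: 37 − 21 = 16 days. If the delay is counted from the permitted Day 23, the earliest day is 23 + 15 = Day 38.

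**3. Does criterion 8 matter?** Criteria 1 to 5 and 7 all need Grade 3 or higher. Criterion 6 needs discontinuation during Cycle 1. For a drug-related Grade 2 event held under Table 7, criterion 8 is therefore the only route to a DLT unless treatment is stopped in Cycle 1. Long holds are plausible: section 5.7.1 gives oral steroids for Grade 2 colitis lasting more than 3 days, with a taper of at least 4 weeks once it improves, and section 5.5.2 bars restart until the glucocorticoid dose is below 10 mg daily.

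**4. Cohort calendar at one subject per week.**
- Three subjects dosed on calendar days 1, 8 and 15. The third reaches Day 21 on calendar day 35, when the three are on Days 35, 28 and 21. None can yet have met criterion 8.
- If the next level opens at once, its subjects are dosed on the third subject's Days 22, 29 and 36: three exposed before Day 37.
- If three more are needed and are dosed on calendar days 22, 29 and 36 at the earliest, the sixth reaches Day 21 on calendar day 56. The first three are then on Days 56, 49 and 42, past Day 37; only the second three (Days 35, 28, 21) can have a pending event.

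**5. Illustration.** The documents give no rates, so these are assumed. Let *a* be the DLT rate from criteria 1–7, *b* the rate from criterion 8 alone, with independent subjects and decisions always taken at Day 21.
- 0/3 at Day 21: (1−a)³.
- 0/3 at Day 21, then at least one late DLT: (1−a)³ − (1−a−b)³.
- Of these, still cleared at 1/6 (one late DLT, then 0/3): 3b(1−a−b)⁵.
- 1/6 at Day 21 that becomes 2/6 or worse (late event in the second three): 3a(1−a−b)² × [(1−a)³ − (1−a−b)³].

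For a = 0.10, b = 0.05: 0.729 − 0.614 = 0.115; 3 × 0.05 × 0.85⁵ = 0.067; difference 0.048. The last term is 0.30 × 0.7225 × 0.115 = 0.025.

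| a | b | 0/3 at Day 21 | later ≥1 DLT | still clears at 1/6 | would not clear | 1/6 becomes ≥2/6 |
|---|---|---|---|---|---|---|
| 0.10 | 0.02 | 0.729 | 0.048 | 0.032 (67%) | 0.016 | 0.011 |
| 0.10 | 0.05 | 0.729 | 0.115 | 0.067 (58%) | 0.048 | 0.025 |
| 0.10 | 0.10 | 0.729 | 0.217 | 0.098 (45%) | 0.119 | 0.042 |
| 0.20 | 0.02 | 0.512 | 0.037 | 0.017 (46%) | 0.020 | 0.014 |
| 0.20 | 0.05 | 0.512 | 0.090 | 0.036 (40%) | 0.055 | 0.030 |
| 0.20 | 0.10 | 0.512 | 0.169 | 0.050 (30%) | 0.119 | 0.050 |

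Differences are taken before rounding. Percentages are of the column to their left.

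**The case against.** The strongest reply is that escalation is not automatic. Section 7.1.2.1 has the sponsor and investigators review whether escalation is appropriate before a cohort opens, the trial is open-label, and a hold on both drugs would be visible to people who know criterion 8. They may well wait. This stands as a limit on the risk, but it is discretion; the written rule for 0/3 is to escalate.

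Several stronger readings are tempting, and the documents do not support them:
- **That the 35- and 47-week figures prove that decisions fall at Day 21.** They do not. Scenario 1 enrols 52 subjects in 52 weeks with no gap between the four Part A cohorts, so that timeline cannot show when cohort decisions are taken. The case rests on sections 5.2.2, 7.1.2.1 and 8.5.1. Section 8.5.1 is itself an analysis-set definition and does not bar counting a later DLT in a subject already included.
- **That every 0/3 later changed is a wrong escalation.** A result of 1/3 adds three subjects and may still clear at 1/6.
- **That replacement under section 5.2.4 also causes early escalation.** A subject with one of three Cycle 1 SD-101 doses held has received 67%, below the 90% limit, and without a DLT is replaced. A replacement dosed at the earliest on that subject's Day 22 reaches Day 21 on the original subject's Day 42, after Day 37. The harm is a needless or wrong replacement.
- **That Grade 2 colitis must delay Cycle 2 past Day 36.** Restart depends on the steroid dose falling below 10 mg, not on the end of the taper, and no starting dose is given.
- **That the monkey data predict colitis at the trial doses.** Large-intestine inflammation occurred at 75 and 150 mg/kg and resolved. None was seen at 25 mg/kg, and section 4.2.2.3 puts no-effect exposure at 2-fold (AUC) to 2.5-fold (Cmax) that expected at 700 mg.
- **That Parts B and C or the final DLT rate are wrong.** Table 6 counts are reassessed continuously and pool escalation and confirmation subjects at the selected dose. Criterion 8 events will be known by the final table.

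**Conclusion.** The conflict is real and lies between stated rules on the primary endpoint. Criterion 8 cannot be met until at least 16 days after the DLT window closes, and no rule makes a Part A decision wait. A dose level can be cleared at 0/3 or 1/6 while an event that the plan itself defines as a DLT is pending.

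The size is unknown, because the frequency of criterion 8 events is not given. Under the assumed rates in the table, the chance per dose level of clearing on 0/3 and failing on complete data runs from about 0.02 to 0.12, with a further 0.01 to 0.05 from 1/6. These are upper bounds for those rates, since they assume that nobody ever waits. The timing conflict does not depend on them. The effect is essentially confined to Part A escalation. It should be fixed: the change is small and removes a safety ambiguity in a first-in-human trial.

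**What to change.** Leave the DLT list as it is and set the decision time.
- **5.2.2:** state that criterion 8 is assessed beyond Day 21 for toxicity arising in Cycle 1, and name the day from which the delay is counted (Day 22 gives Day 37).
- **5.2.1.2.1:** allow a Part A cohort decision only when each subject has had a DLT, or has completed 21 days and has started Cycle 2, come off treatment for a reason unrelated to study drug, or, if on a drug-related hold, reached Day 37.
- **5.2.1.2.2:** until then, count a held subject among those not yet evaluable when applying the enrolment limit.
- **5.2.4:** do not replace a held subject before that point.
- **8.5.1:** match the DLT-evaluable definition.

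The cost is an amendment to wording and a wait of up to 16 days, only in cohorts with a drug-related hold at Day 21. Other cohorts wait at most the day or two until Cycle 2 is given. No extra subjects or procedures are required by the waiting rule itself.

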5.2.3 Guidelines for Dose Modifications

5.2.3.1 Dose Modification

The Common Terminology Criteria for Adverse Events version 4.0 (CTCAE 4.0) must be used to grade the severity of adverse events. If appropriate, the Investigator may attribute each toxicity event to MK-1966 or SD-101 alone or to the combination arm.

Part A

Subjects will continue at their enrolled dose for the duration of their participation. Holding of one agent and not the other agent is appropriate if, in the opinion of the Investigator, the toxicity is clearly related to one of the study drugs. If, in the opinion of the Investigator, the toxicity is related to the combination of two agents, both drugs should be held.

Parts B and C

Dose modifications should be made according to [Table 7](#). If a dose reduction for toxicity occurs with any agent, the dose may not be re-escalated. Dose modifications are always based on the previous cycle.

Subjects may have 1 dose modification to MK-1966 or SD-101 throughout the course of the study. If further toxicity occurs or the criteria for resuming treatment are not met, the subject must be discontinued from the agent. If a subject experiences several toxicities and there are conflicting recommendations, follow the most conservative dose adjustment recommended (dose reduction or holding as appropriate to the most severe toxicity).

Reduction or holding of one agent and not the other agents is appropriate if, in the opinion of the Investigator, the toxicity is clearly related to one of the study drugs. If, in the opinion of the Investigator, the toxicity is related to the combination of two agents, both drugs should be held or reduced according to recommended dose modifications.

If in the opinion of the Investigator dose reduction is recommended, either agent can be reduced 1 dose level following consultation with the Sponsor. Only 1 dose reduction (of either agent) is permitted for each subject. If additional dose reduction is warranted, then the subject should be discontinued from the study. Both MK-1966 and SD-101 may only be reduced to the next lowest dose being explored in this study (i.e., MK-1966 210 mg would be reduced to 70 mg). Neither agent may be reduced below the lowest dose being tested in this protocol (MK-1966: 70 mg; SD-101: 1 mg).

Exceptional circumstances to following the dose modification tables below may be considered after consultation with the Sponsor.

In all study Parts, both MK-1966 and SD-101 will be held for the adverse events described below in [Table 7](#).

Table 7 MK-1966 and SD-101 Dose Modification Guidelines for Drug-Related Adverse Events

Toxicity	Hold Treatment For	Timing for Restarting Treatment	Treatment Discontinuation
Diarrhea/Colitis	Grade 2-3	Toxicity resolves to Grade 0-1	Toxicity does not resolve within 12 weeks of last dose or inability to reduce corticosteroid to 10 mg or less of prednisone or equivalent per day within 12 weeks
	Grade 4	Permanently discontinue	Permanently discontinue
AST, ALT, or Increased Bilirubin	Grade 2	Toxicity resolves to Grade 0-1	Toxicity does not resolve within 12 weeks of last dose
	Grade 3-4	Permanently discontinue (see exception below) ^a	Permanently discontinue
Type 1 diabetes mellitus (if new onset) or Hyperglycemia	T1DM or Grade 3-4	Hold SD-101 and MK-1966 for new onset Type 1 diabetes mellitus or Grade 3-4 hyperglycemia associated with evidence of beta cell failure	Resume SD-101 and MK-1966 when patients are clinically and metabolically stable

Toxicity	Hold Treatment For	Timing for Restarting Treatment	Treatment Discontinuation
Hypophysitis	Grade 2-4	Toxicity resolves to Grade 0-1. Therapy with SD-101 and MK-1966 can be continued while endocrine replacement therapy is instituted	Toxicity does not resolve within 12 weeks of last dose or inability to reduce corticosteroid to 10 mg or less of prednisone or equivalent per day within 12 weeks
Hyperthyroidism	Grade 3	Toxicity resolves to Grade 0-1	Toxicity does not resolve within 12 weeks of last dose or inability to reduce corticosteroid to 10 mg or less of prednisone or equivalent per day within 12 weeks
	Grade 4	Permanently discontinue	Permanently discontinue
Hypothyroidism		Therapy with SD-101 and MK-1966 can be continued while thyroid replacement therapy is instituted	Therapy with SD-101 and MK-1966 can be continued while thyroid replacement therapy is instituted
Infusion Reaction	Grade 2 ^b	Toxicity resolves to Grade 0-1	Permanently discontinue if toxicity develops despite adequate premedication
	Grade 3-4	Permanently discontinue	Permanently discontinue
Injection Reaction	≥ Grade 3	Toxicity resolves to Grade 0-1	Toxicity does not resolve within 12 weeks of last dose
Pneumonitis	2	Toxicity resolves to Grade 0-1	Toxicity does not resolve within 12 weeks of last dose or inability to reduce corticosteroid to 10 mg or less of prednisone or equivalent per day within 12 weeks
	3-4 (or recurrent Grade 2)	Permanently discontinue	Permanently discontinue
Renal Failure or Nephritis	2	Toxicity resolves to Grade 0-1	Toxicity does not resolve within 12 weeks of last dose or inability to reduce corticosteroid to 10 mg or less of prednisone or equivalent per day within 12 weeks
	3-4	Permanently discontinue	Permanently discontinue
ANC	≤1500 cells/mcL	≥ 1500 cells/mcL	ANC does not increase ≥ 1500 cells/mcL within 12 weeks

Toxicity	Hold Treatment For	Timing for Restarting Treatment	Treatment Discontinuation
All Other Drug-Related Toxicity ^c	3 or Severe	Toxicity resolves to Grade 0-1	Toxicity does not resolve within 12 weeks of last dose or inability to reduce corticosteroid to 10 mg or less of prednisone or equivalent per day within 12 weeks
	4	Permanently discontinue	Permanently discontinue

AE = adverse event; ALT = alanine transaminase; AR = adverse reaction; AST = aspartate transaminase; T1DM = type 1 diabetes mellitus.

Note: Permanently discontinue for any severe or Grade 3 (Grade 2 for pneumonitis) drug-related AE that recurs or any life-threatening event.

^a For patients with liver metastasis who begin treatment with Grade 2 AST or ALT, if AST or ALT increases by greater than or equal to 50% relative to baseline and lasts for at least 1 week then patients should be discontinued.

^b If symptoms resolve within one hour of stopping drug infusion, the infusion may be restarted at 50% of the original infusion rate (e.g., from 100 mL/hr to 50 mL/hr). Otherwise dosing will be held until symptoms resolve and the subject should be premedicated for the next scheduled dose. Refer to Table 8– Infusion Reaction Treatment Guidelines for further management details.

^c Patients with intolerable or persistent Grade 2 drug-related AE may hold study medication at physician discretion. Permanently discontinue study drug for persistent Grade 2 adverse reactions for which treatment with study drug has been held, that do not recover to Grade 0-1 within 12 weeks of the last dose.

